## 7.2 Imaging Assessment of Efficacy

Standard anatomic MRI in conjunction with clinical evaluation such as neurologic status and corticosteroid use, remains the key determinant of response to therapy and the evaluation of tumor recurrence for low grade glioma. Increase in contrast enhancement, worsening cerebral edema, and increased mass effect are traits of malignant transformation. Acquiring tissue samples to confirm tumor upgrade, although considered the “gold standard” for determining the presence of viable tumor, can result in both false positives and negatives that relate to sampling error. Evaluating response in low-grade glioma by radiographic imaging is an accepted means of determining response and is the standard by which NIH grant-funded brain tumor consortiums operate.

The majority of previously untreated LGG are non-enhancing on the post-Gadolinium T1-weighted images. This means that the primary analysis is based upon the interpretation of regions with hyperintensity on T2-weighted images, which are unable to distinguish edema from invasive tumor. After treatment, some lesions become enhancing, but that can be due either to treatment effect or to the presence of recurrent, progressive tumor. This complicates the interpretation of anatomic images and has motivated the search for alternative imaging modalities.

The recent review of response criteria for LGG performed by the RANO working group made the clear recommendation that alternative imaging approaches should be considered in evaluating such lesions (van den Bent, Wefel et al. 2011). Our previous research has made a concerted effort to determine which non-invasive metabolic and physiological imaging parameters are associated with residual disease and to identify markers that predict malignant transformation by using image guided tissue samples from patients with recurrent LGG (Bian, Khayal et al. 2009). This analysis has confirmed the relationship between *in vivo* tissue markers of increased blood volume, restricted diffusion and increased metabolite levels with histological evidence of tumor progression.

Of particular interest for the proposed study are the results from applying physiological and metabolic imaging methods to monitor response to therapy in the ongoing phased II clinical trial of everolimus for patients with recurrence. These are applying MR spectroscopic imaging (MRSI), Dynamic Contrast Enhanced (DCE) or Dynamic Susceptibility Contrast (DSC) imaging and diffusion-weighted imaging (DWI) in conjunction with standard anatomic MRI (Bian, Khayal et al. 2009). Early analysis of these data has revealed that the capillary density and vascular permeability measures estimated from DCE-MRI at 4 and 6 months after the start of everolimus decreased significantly in patients with stable disease but not in those with progressive disease. This suggests that decreased angiogenesis may represent an early marker of response to everolimus.

While metabolic imaging has not yet been widely evaluated for evaluation of response to temozolomide in LGG, we have shown that baseline and early changes in metabolites assessed using H-1 MRSI are predictive of outcome for patients with high-grade glioma who are being

treated with therapies that include temozolomide (Nelson 2011). We have also shown in pre-clinical models using C-13 metabolic imaging that early changes in the lactate/pyruvate ratio are associated with response to treatment with temozolomide (Park, Bok et al. 2011). This suggests that the combination of metabolic and physiological imaging will be valuable for this study.

### 7.2.1 Imaging Protocol

Data will be acquired using 3T clinical or research scanners and multi-channel phased array head coils in order to provide the highest possible sensitivity. These scanners are kept at similar software and hardware revisions and are connected by the PACS network. The following is the advanced imaging protocol currently being used for patients with glioma.

- a) Calibration/Localization images: These include a 3-D localizing scan to define the graphical prescription and low resolution (64x64 matrix with 26cm FOV) multi-slice gradient echo calibration images obtained with minimal contrast and with the data from different elements of the multi-channel head coil reconstructed separately. The individual images provide estimates of the coil sensitivities for use in reconstructing parallel imaging reconstructions of subsequent anatomical and spectroscopic imaging data to accelerate acquisition times. (Tacq < 2min)
- b) T2 FLAIR images: 3-D sagittally acquired images with typical parameters of TR/TE/TI = 6000/134/2200ms, with 1mm isotropic voxels (256x256 matrix and 26cm FOV) and 3-fold parallel imaging acceleration, reformatted to axial and coronal planes for analysis and clinical interpretation. (Tacq = 8 min)
- c) Pre-contrast 3D T1 IR-SPGR images: 3-D axial T1- weighted, inversion recovery prepared, spoiled gradient echo images with typical parameters TR/TE/TI = 8/2/400ms, flip angle 15°, 2-fold parallel imaging acceleration, and 1mm in plane resolution (256x256 matrix, 24cm FOV) with 1.5mm slice thickness. (Tacq = 4 min)
- d) Diffusion-weighted Imaging (DWI): Diffusion weighted spin echo single shot echo planar images with  $b = 1000 \text{ s/mm}^2$ , 6 gradient directions, 4 NEX, TR/TE = 7000/76ms, 128x128 matrix with 22cm FOV, 2-fold parallel imaging acceleration to reduce distortion, and 3-4mm slice thickness. (Tacq = 4 min)
- e) Lactate-edited 3-D MRSI: Water suppressed, lactate-edited H MRSI with automated PRESS volume and out of voxel saturation bands prescription, and 2-D phase encoding and flyback EPSI encoding to cover the lesion, surrounding tissue, and as much of the contralateral normal-appearing brain as possible. Typical parameters are TR/TE=1000-1100/144, matrix size 16x16x16 and nominal spatial resolution 1cc (10min)
- f) Perfusion-weighted Imaging (PWI): Dynamic gradient-echo, single-shot echo-planar images acquired during the bolus of a Gadolinium contrast agent, 0.1mm/Kg, injection speed 5ml/s. Typical acquisition parameters are TR/TE/Flip = 1500ms/35ms/35°, 80 time points, 22 slices,

---

4mm slice thickness, 26cm FOV, 128x128 matrix, and 2-fold parallel imaging acceleration factor to reduce distortion (Tacq = 2min).

g) Post-contrast anatomic images: These will include 3D T1 IR-SPGR images as described above and T1-weighted spin echo images as a clinical reference. (Tacq = 10 min)

In addition to the scans described above that are used for routine follow-up, MR examinations acquired immediately prior to surgery include T2-weighted FSE anatomical images and DTI images prior to gadolinium injection with parameters as follows:

h) T2-weighted FSE: 3-D axial images with typical parameters of TR/TE/ETL = 4300/102/33, with 24cm FOV, 256x256 matrix, 2-fold parallel imaging acceleration, and 1.5mm slice thickness. (Tacq = 9 min)

i) Diffusion Tensor Imaging (DTI): Diffusion-weighted single-shot echo planar spin-echo pulse sequence will be employed with 55 diffusion-gradient directions, with isotropic 2.2 mm voxel resolution, FOV 280x280 mm, 128x128 matrix, 2.2-mm interleaved slices with no gaps, at  $b=2000$  s/mm^2. (Tacq = 7 min)

## 7.2.2 Imaging Time Points

Standard anatomic MR imaging will be performed as outlined in Table 7. The full imaging examination described above will optionally be performed at baseline, at the end of cycles 2 and 6, and at the time of suspected progression. The anatomic imaging components are standard of care, with the other parts being research add-ons. After the end of treatment and prior to progression, patients will be followed with anatomic imaging alone. The goal will be to determine whether the parameters estimated from advanced imaging are early predictors of response to therapy.

## 7.2.3 Imaging Response Criteria

Imaging assessment will be done by a UCSF neuro-oncologist according to the RANO criteria for low-grade gliomas (van den Bent, et al, Lancet Oncology 2011):

**Complete response:** Complete response requires all the following criteria compared with the baseline scan:

- (1) Complete disappearance of the lesion on T2 or FLAIR imaging (if enhancement had been present, it must have resolved completely);
- (2) no new lesions, no new T2 or FLAIR abnormalities apart from those consistent with radiation effects, and no new or increased enhancement;
- (3) patients must be off corticosteroids or only on physiological replacement doses;
- (4) patients should be stable or improved clinically

**Partial response:** Partial response requires all of the following criteria compared with the baseline scan:

- (1) greater than or equal to 50% decrease in the product of perpendicular diameters of the lesion on T2 or FLAIR imaging sustained for at least 4 weeks compared with baseline;
- (2) no new lesions, no new T2 or FLAIR abnormalities apart from those consistent with radiation effects, and no new or increased enhancement; and
- (3) patients should be on a corticosteroid dose that should not be greater than the dose at time of baseline scan, and should be stable or improved clinically

**Minor response:** Minor response requires the following criteria compared with baseline:

- (1) a decrease of the area of non-enhancing lesion on T2 or FLAIR MR imaging between 25% and 50% compared with baseline;
- (2) no new lesions, no new T2 or FLAIR abnormalities apart from those consistent with radiation effect, and no new or increased enhancement; and
- (3) patients should be on a corticosteroid dose that should not be greater than the dose at time of baseline scan, and should be stable or improved clinically

**Stable disease:** Stable disease is present if the changes do not qualify for complete, partial, or minor response, or progression and requires:

- (1) stable area of non-enhancing abnormalities on T2 or FLAIR imaging;
- (2) no new lesions, no new T2 or FLAIR abnormalities apart from those consistent with radiation effect, and no new or increased enhancement; and
- (3) patients should be on a corticosteroid dose that should not be greater than the dose at time of baseline scan, and should be stable or improved clinically

**Progression:** Progression is defined by any of the following:

---

- (1) development of new lesions or increase of enhancement (radiological evidence of malignant transformation);
- (2) a 25% increase of the T2 or FLAIR non-enhancing lesion on stable or increasing doses of corticosteroids compared with baseline scan or best response after initiation of therapy, not attributable to radiation effect or to comorbid events;
- (3) definite clinical deterioration not attributable to other causes apart from the tumour, or decrease in corticosteroid dose; or
- (4) failure to return for evaluation because of death or deteriorating condition, unless caused by documented non-related disorders

## 7.3 Pathology and Molecular Assessments

Pathology must be reviewed in the UCSF pathology department.

### 7.3.1 Obtaining Tissues Samples:

- The UCSF Neurosurgery Tissue Bank has a general consent that patients sign to authorize release of their samples from previous surgeries at outside institutions.
- Unstained slides and/or paraffin tissue blocks, along with a pathology report, are sent to UCSF -- c/o one of the NeuroOnc study coordinators or directly to the Neurosurgery tissue bank manager (currently [name])

#### Preparation of tissue samples:

- Once received, samples are logged into the Tissue Bank computer system and assigned an SF#.
- If paraffin blocks are provided unstained slides will be prepared from these.
- If H&E slides are not provided they will be prepared from unstained slides.

All staining and immunohistochemistry will be performed at the UCSF Brain Tumor Research Center Biomarkers Laboratory in the Neurosurgery Tissue Bank or in the UCSF Department of Pathology

#### Review of tissue samples:

- Pathology Materials Required for Review:
  - A copy of the Pathology Reports and the Operative Reports.

- A Protocol Specific Pathology Submission Form.
- A neuropathologist will review all H&E slides and will determine if the provided tissue is adequate / appropriate for the study and the best block for additional assays will be selected.
- In general, one to two representative H&E stained slides will be reviewed.

### **7.3.2 Treatment Selection Factors**

Patient treatment will be selected by 1p/19q chromosomal status as determined by fluorescence in-situ hybridization (FISH) and/or ATRX mutation as determined by immunohistochemistry. Briefly, deletion of 1p and 19q will be determined based on the determination of the ratio of test probe to reference probe. A deletion is defined as a ratio of test probe to reference probe <0.8 and >15% of the cells showing a reference:target ratio of at least 2:1. Patients whose tumor is 1p/19q intact will be further selected by tumor PI3K/mTOR pathway activation (Pathact) as determined by immunohistochemistry for phospho-PRAS40. Pathway activation will be defined as a score of greater than or equal to 1 based on an assessment of tumor cells immunopositive for phospho-PRAS40 as follows: 0, no significant positive staining in tumor cells; 1, 1-33% of tumor cells positive; 2, 33-66% positive; 3, greater than 66% tumors cells positive. A similar scoring system was used previously to assess pathway activation in low grade glioma [McBride et al. 2010]. Based on this study which identified 18 of 35 patients with p-PRAS40-positive tumors, we anticipate approximately 50% of newly diagnosed low-grade gliomas will be Pathact regardless of 1p/19q status.

The ATRX mutation typically results in a truncated protein and abrogated protein expression [Heaphy CM 2012; Liu XY 2012]. Thus, immunohistochemistry for ATRX can be performed and loss of immunostaining can be used as a surrogate for detecting ATRX mutations. For the evaluation of ATRX immunohistochemistry, only nuclear staining is assessed. A tumor is considered to be ATRX mutant when there is loss of ATRX in all tumor cell nuclei while nuclear positivity is present in non-neoplastic cells, including blood vessels, microglia, reactive astrocytes, and entrapped neurons. This assay will be performed clinically in a CLIA-certified laboratory, interpreted by a board-certified neuropathologist, and reported in the clinical chart.

### **7.3.3 Molecular and Biologic Correlative Studies**

#### **7.3.3.1A Immunohistochemical Assays**

See Appendix 2, Section A for details.

#### **7.3.3.1B Molecular Analyses**

See Appendix 2, Section B for details.

#### **7.3.3.2 Genomic Analyses: Custom capture Approach**

See Appendix 2, Section C for details.

### **7.4 Quality of Life Assessment**

Very little data is available prospectively assessing quality of life in patients with low-grade glioma, and it is increasingly appreciated that this is an important aspect of caring for patients with brain tumors. As such, patients on Arms 1 and 3 (those receiving everolimus as monotherapy) will be asked to participate in a quality of life component of the study, filling out questionnaires at enrollment and at the end of every 6 cycles during treatment (at the time of the MRI and clinic visit), then at 1 year post-completion of treatment, again associated with the corresponding MRI and clinic visit, or at the time of tumor progression if that occurs sooner than 1 year post-completion of treatment. Participation in this portion of the study will be voluntary. The survey instruments used will be the FACT-Br and the MDASI-BT, both of which are validated in patients with brain tumors (Weitzner, Meyers, et al. 1995; Liu, Solheim, et al. 2009; Armstrong, Gning, et al. 2009). Whenever possible, patients should fill out the questionnaires at each visit *prior to* meeting with the physician to discuss MRI results.

## **8 Safety monitoring and reporting**

The study will use the [CTCAE v4.0](#) for reporting of non-hematologic adverse events and modified criteria for hematologic adverse events. See Section 6.2 for details.

### **8.1 Definitions of Adverse Events**

#### **8.1.1 Adverse Event**

An adverse event (also known as an adverse experience) is defined as any untoward medical occurrence associated with the use of a drug in humans, whether or not considered drug related. More specifically, an adverse event (can be any unfavorable and unintended sign (e.g., an abnormal laboratory finding), symptom, or disease temporally associated with the use of a drug, without any judgment about causality. An adverse event can arise from any use of the drug (e.g., off-label use, use in combination with another drug) and from any route of administration, formulation, or dose, including an overdose.

#### **8.1.2 Adverse reaction**

An adverse reaction is defined as any adverse event caused by the use of a drug. Adverse reactions are a subset of all suspected adverse reactions for which there is reason to conclude that the drug caused the event.

### **8.1.2.1 Suspected**

A suspected adverse reaction is defined as any adverse event for which there is a reasonable possibility that the drug caused the adverse event. For the purposes of IND safety reporting, “reasonable possibility” indicates that there is evidence to suggest a causal relationship between the drug and the adverse event. A suspected adverse reaction implies a lesser degree of certainty about causality than an adverse reaction.

### **8.1.2.2 Unexpected**

An adverse event or suspected adverse reaction is considered *unexpected* if it is not listed in the investigator brochure or package insert(s), or is not listed at the specificity or severity that has been observed, or, if an investigator brochure is not required or available, is not consistent with the risk information described in the general investigational plan or elsewhere in the current application.

“Unexpected,” as used in this definition, also refers to adverse events or suspected adverse reactions that are mentioned in the investigator brochure as occurring with a class of drugs or as anticipated from the pharmacological properties of the drug, but are not specifically mentioned as occurring with the particular drug under investigation.

Adverse events that would be anticipated to occur as part of the disease process are considered *unexpected* for the purposes of reporting because they would not be listed in the investigator brochure. For example, a certain number of non-acute deaths in a cancer trial would be anticipated as an outcome of the underlying disease, but such deaths would generally not be listed as a suspected adverse reaction in the investigator brochure.

Some adverse events are listed in the Investigator Brochure as occurring with the same class of drugs, or as anticipated from the pharmacological properties of the drug, even though they have not been observed with the drug under investigation. Such events would be considered *unexpected* until they have been observed with the drug under investigation. For example, although angioedema is anticipated to occur in some patients exposed to drugs in the ACE inhibitor class and angioedema would be described in the investigator brochure as a class effect, the first case of angioedema observed with the drug under investigation should be considered *unexpected* for reporting purposes.

### **8.1.2.3 Serious**

An adverse event or suspected adverse reaction is considered *serious* if, in the view of either the investigator or sponsor, it results in any of the following outcomes:

- Death
- Life-threatening adverse event
- Inpatient hospitalization or prolongation of existing hospitalization
- A persistent or significant incapacity or substantial disruption of the ability to conduct normal life function
- Congenital anomaly/birth defect

Important medical events that may not result in death, are life-threatening, or require hospitalization may be considered serious when, based upon appropriate medical judgment, they may jeopardize the patient or subject and may require medical or surgical intervention to prevent one of the outcomes listed in this definition. Examples of such medical events include allergic bronchospasm requiring intensive treatment in an emergency room or at home, blood dyscrasias or convulsions that do not result in inpatient hospitalization, or the development of drug dependency or drug abuse.

#### 8.1.2.4 Life-threatening

An adverse event or suspected adverse reaction is considered *life-threatening* if, in the view of either the investigator or sponsor, its occurrence places the patient or subject at immediate risk of death. It does not include an adverse event or suspected adverse reaction that, had it occurred in a more severe form, might have caused death.

### 8.2 Recording of an Adverse Event

All grade 3 and above adverse events will be entered into OnCore®, whether or not the event is believed to be associated with use of the study drug. Data about these events and their severity will be recorded using the NCI CTCAE v4.0.

The Investigator will assign attribution of the possible association of the event with use of the investigational drug, and this information will be entered into OnCore® using the classification system listed below:

Relationship	Attribution	Description
Unrelated investigational drug/intervention	Unrelated	The AE is clearly NOT related to the intervention
	Unlikely	The AE is doubtfully related to the intervention
Related to investigational drug/intervention	Possible	The AE may be related to the intervention
	Probable	The AE is likely related to the intervention
	Definite	The AE is clearly related to the intervention

Signs or symptoms reported as adverse events will be graded and recorded by the Investigator according to the CTCAE. When specific adverse events are not listed in the CTCAE they will be graded by the Investigator as *none, mild, moderate* or *severe* according to the following grades and definitions:

- Grade 0      No AE (or within normal limits)
- Grade 1      Mild; asymptomatic or mild symptoms; clinical or diagnostic observations only; intervention not indicated
- Grade 2      Moderate; minimal, local, or noninvasive intervention (e.g., packing, cautery) indicated; limiting age-appropriate instrumental activities of daily living (ADL)
- Grade 3:      Severe or medically significant but not immediately life-threatening; hospitalization or prolongation of hospitalization indicated; disabling; limiting self-care ADL
- Grade 4:      Life-threatening consequences; urgent intervention indicated
- Grade 5:      Death related to AE

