**Secondary Endpoints (for all arms):**

- 1) Median and distribution of overall survival (OS) and PFS
- 2) Objective Response Rate (ORR)
- 3) Number of adverse events related to combination treatment
- 4) Rate of Reduction in Seizures (as outlined in van den Bent, Wefel *et al.* 2011)

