### 6.2.2.2 Management of skin toxicity

For patients with grade 1 toxicity, no specific supportive care is usually needed or indicated. Rash must be reported as an AE. Patients with grade 2 or higher toxicity may be treated with the following suggested supportive measures at the discretion of the investigator: oral minocycline, topical tetracycline, topical clindamycin, topical silver sulfadiazine, diphenhydramine, oral prednisolone (short course), topical corticosteroids, or pimecrolimus.

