### **8.4    Adverse Events Monitoring**

All adverse events, whether or not unexpected, and whether or not considered to be associated with the use of the study drug, will be entered into OnCore®, as noted above.

The Investigator will assess all adverse events and determine reportability requirements to the UCSF Data and Safety Monitoring Committee (DSMC) and UCSF's Institutional Review Board, the Committee on Human Research (CHR); and, when the study is conducted under an Investigational New Drug Application (IND), to the Food and Drug Administration (FDA) if it meets the FDA reporting criteria..

All adverse events entered into OnCore® will be reviewed by the Helen Diller Family Comprehensive Cancer Center Site Committee on a weekly basis. The Site Committee will review and discuss at each weekly meeting the selected toxicity, the toxicity grade, and the attribution of relationship of the adverse event to the administration of the study drug(s).

All grade(s) 3-5 adverse events entered into OnCore® will be reviewed on a monthly basis at the Site Committee meetings. The Site Committee will review and discuss the selected toxicity, the toxicity grade, and the attribution of relationship of the adverse event to the administration of the study drug(s).

In addition, all suspected adverse reactions considered “serious” entered into OnCore®, will be reviewed and monitored by the Data and Safety Monitoring Committee on an ongoing basis and discussed at DSMC meetings, which take place every six weeks.

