## 9.6 Evaluation of Safety

---

Analyses will be performed for all patients having received at least one dose of study drug. The study will use the NCI CTCAE v4.0. Safety and tolerability will be assessed by incidence, severity, and changes from baseline of all relevant parameters including AEs, laboratory values, and vital signs.

AEs will be coded using the latest available version of the Medical Dictionary for Regulatory Activities (MedDRA). AEs will be summarized for each treatment arm by the number and percentage of patients who experienced the event, according to system organ class (SOC) and preferred term (PT). Additional summaries will also be provided by severity grade and relationship to study drug, and for SAEs and events resulting in the permanent discontinuation of therapy. A subject reporting multiple cases of the same AE will be counted once within each SOC and similarly counted once within each PT, and AEs will be graded by worst severity grade. Unless specified otherwise, the denominator for these calculations will be based on the number of patients in each treatment arm who receive at least one dose of study drug, irrespective of the total number of doses administered.

Vital sign results (systolic and diastolic blood pressure, pulse, respiration, and body temperature) will be summarized descriptively for each scheduled and unscheduled protocol time point. Changes will be calculated relative to the assessments at baseline.

The changes in hematology, chemistry, and other laboratory values will be summarized descriptively for each scheduled and unscheduled protocol assessment time point. Changes will be calculated relative to the values collected at baseline. Data listings of all laboratory data collected during the study will be presented. Laboratory values outside normal limits will be identified in data listings and will include flags for high and low values.

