#### **Adverse Event Review and Monitoring**

All grade(s) 3-5 adverse events, whether or not unexpected, and whether or not considered to be associated with the use of the study drug, will be entered into OnCore®, UCSF's Clinical Trial Management System.

All grade(s) 3-5 adverse events entered into OnCore® will be reviewed on a monthly basis at the Site Committee meetings. The Site Committee will review and discuss the selected toxicity, the toxicity grade, and the attribution of relationship of the adverse event to the administration of the study drug(s).

In addition, all suspected adverse reactions considered “serious” entered into OnCore®, will be reviewed and monitored by the Data and Safety Monitoring Committee on an ongoing basis and discussed at DSMC meetings, which take place every six weeks.

If a death occurs during the treatment phase of the study or within 30 days after the last administration of the study drug(s) and it is determined to be related either to the study drug(s) or to a study procedure, the Investigator or his/her designee must notify the DSMC Chair within **1 business day** of knowledge of this event. The contact may be by phone or e-mail.

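### Sections 8.2 and 8.4 and Appendix 3 give different grade limits for entering adverse events in the database, and the safety tables and secondary endpoint 3 do not say which applies

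*Combined protocol and SAP*

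**What the plan says.** Three places in the combined protocol and SAP tell staff which adverse events go into OnCore.

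- Section 8.2: "All grade 3 and above adverse events will be entered into OnCore", whatever the attribution.
- Appendix 3 (Adverse Event Review and Monitoring): "All grade(s) 3-5 adverse events, whether or not unexpected", again whatever the attribution.
- Section 8.4: "All adverse events, whether or not unexpected, and whether or not considered to be associated with the use of the study drug" are to be entered, with no grade limit. The sentence refers back to the earlier recording rule, which is the grade 3+ one.

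The uses of these data carry no grade floor. Section 3 lists secondary endpoint 3 as "Number of adverse events related to combination treatment". Section 9.6 states "AEs will be summarized for each treatment arm by the number and percentage of patients who experienced the event", by system organ class and preferred term, with further summaries by severity grade, by relationship and for events leading to permanent discontinuation. For laboratory values, 9.6 adds: "Data listings of all laboratory data collected during the study will be presented".

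**The concern.** A coordinator working from 8.2 or Appendix 3 has an instruction to enter grades 3-5 and none to enter grades 1-2. A coordinator working from 8.4 enters everything. The same patient could yield two different event counts, each defensible from the text.

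Secondary objective 3, delineating the safety profile of everolimus plus temozolomide in Arm 2, depends on this count. Section 2.4 describes earlier experience with the combination partly through mild events such as fatigue, rash and mucositis. Under grade 3+ entry, events of that kind would drop out of the database. The incidence table and the endpoint count would look like all-grade results without being so.

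**Working it through.** No design figure (sample size, alpha, power) enters this point. The check is a comparison of the text, followed by simple arithmetic on what would be lost.

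**Step 1. The entry rules and the analyses side by side.**

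| Place | Function | Grades covered |
|---|---|---|
| 8.2 | entry rule | 3-5 |
| Appendix 3 | entry rule | 3-5 |
| 8.4 | entry rule | all |
| 9.6 | incidence, severity and relationship tables | no floor |
| Secondary endpoint 3 | related-event count | no floor |
| 10.6 | all study data go into OnCore | not stated |

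No section says which entry rule governs, and none limits 9.6 or the endpoint to grade 3 and above.

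**Step 2. Can the back-reference in 8.4 reconcile them?** Suppose it imports the grade 3+ limit. Section 8.4 sets a weekly review of all entered events ("The Site Committee will review and discuss at each weekly meeting the selected toxicity, the toxicity grade") and a separate monthly review of grade 3-5 events. If only grade 3-5 events are entered, the two reviews cover the same events and the split has no purpose. Section 9.6 and endpoint 3 would also have no database source for grade 1-2 clinical events.

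Suppose instead that 8.2 is only a minimum. Then 8.2 and Appendix 3 are incomplete beside 8.4, and staff who read only those sections are not told so. Neither reading makes the three places agree.

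**Step 3. What would be missing under the restrictive reading.** Section 8.2 defines five event grades, 1 to 5 (grade 0 means no event). The entry rule names three, 3 to 5.

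- Grade levels not named: 5 - 3 = 2 (grades 1 and 2).
- In the 9.6 severity summary, 2 of 5 levels would be empty for clinical events. Low-grade laboratory abnormalities would still appear in the laboratory listings.

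Let g be the grade 1-2 share of related clinical events. The recorded share of the all-grade count is 1 - g. The documents do not give g, so these values are assumptions:

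| Assumed g | Recorded share, 1 - g |
|---|---|
| 0.25 | 0.75 |
| 0.50 | 0.50 |
| 0.75 | 0.25 |
| 0.90 | 0.10 |

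**Step 4. Reach.** The primary endpoints, PFS-33 and PFS-38, do not use adverse-event entries. The Section 9.4 rule counts drug discontinuations due to toxicity rather than adverse-event rows, so as written it does not depend on the entry rule. The 9.6 summary of events causing permanent discontinuation could be affected if it is built from adverse-event entries. The grade 2 row of Table 6-6 allows pneumonitis below grade 3 to end in discontinuation, and such an event would have no entry under the grade 3+ rule.

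**The case against.** The strongest reply is that there is no strict contradiction. Grade 3-5 events are a subset of all events, neither 8.2 nor Appendix 3 says that lower grades are excluded, and staff who follow 8.4 satisfy all three places.

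Much of the other text also favours all-grade entry. There is the weekly and monthly review split, and 8.2's own grading scale includes grades 1 and 2. Section 6.2.2.2 says "Rash must be reported as an AE" in a paragraph that opens with grade 1, and 10.6 sends all study data to OnCore. No participating sites are listed, entry uses standardized forms, and the investigator approves them, so one working rule may already be in force. Empty grade 1-2 rows in the severity summary would alert a careful reader.

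Most of this stands as a limit on weight. It makes all-grade entry the likelier intention and leaves the data loss conditional on how staff read 8.2. It does not remove the mismatch: a recording section that names only grade 3 and above gives no instruction to enter lower grades, and Appendix 3 repeats the limit. The clue from empty rows helps with the severity table, but not with the organ-class and preferred-term table or the endpoint count read alone. The forms are not in the documents, so they cannot be relied on to settle the rule.

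**Conclusion.** The concern holds. The entry rule is stated inconsistently, and a named secondary endpoint and the 9.6 adverse-event tables depend on it. That the wording differs is certain. That events would be lost is conditional on staff treating 8.2 and Appendix 3 as the full rule. In that case grades 1 and 2 are empty for clinical events, and the related-event count falls by their share, whose size the documents do not allow one to estimate. This should be corrected, but it does not threaten the primary analysis.

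**What to change.** Use one entry rule in 8.2, 8.4 and Appendix 3. The preferable rule is to enter clinical adverse events of all grades, with grade and attribution, and keep the grade 3-5 limit for the monthly Site Committee review only. This fits 8.4, 9.6 and secondary endpoint 3 as they stand. If Appendix 3 is fixed institutional text, state in 8.2 that 8.2 governs entry for this trial.

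If the sponsor intends grade 3+ capture, that is a choice open to it. In that case correct 8.4 and label the 9.6 adverse-event tables and secondary endpoint 3 as grade 3+ only.

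Relabelling costs almost nothing. All-grade entry costs text edits, more data entry and possibly back-entry: this is Version 6.0, and the documents do not give enrolment status. The documentation list in 7.1.2 names treatment-related toxicities without a grade floor, so sources for the related-event count should exist. It does not name unrelated events, so back-entry of unrelated grade 1-2 events could be incomplete, and the report should say so.
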